HIV	Human immunodeficiency virus
hsCRP	High-sensitivity C-reactive protein
ICF	Informed consent form
ICH	International Conference on Harmonisation
ICH-GCP	International Conference of Harmonisation-Good Clinical Practice

Abbreviation	Definition
IL-1 α	Interleukin-1alpha
IR	Infusion reaction
IRB	Institutional Review Board
IV	Intravenous, intravenously
IUD	Intrauterine device
IP	Investigational Product
LDH	Lactic acid dehydrogenase
mAb	Monoclonal antibody
MedDRA	Medical Dictionary for Regulatory Affairs
NOAEL	No observed adverse effect level
Nt-proBNP	N-terminal pro-B-type natriuretic peptide
PCR	Polymerase chain reaction
PD	Pharmacodynamics
PK	Pharmacokinetics
PT	Preferred term
SAE	Serious Adverse Event
SAP	Statistical Analysis Plan
SCID	Severe Combined Immune Deficiency
SD	Standard deviation
SMC	Safety Monitoring Committee
SOC	System organ class
ULN	Upper limit of normal
WBC	White blood cell
WHO	World Health Organization
WOCBP	Women of childbearing potential

SYNOPSIS

Sponsor: Trellis Bioscience, Inc.	
Study Title: A Phase 1, Double-Blind, Single Ascending Dose Study to Evaluate the Safety, Pharmacokinetics, and Pharmacodynamics of TRL345 in Healthy Volunteers	
Test Product: TRL345	
Name of Active Ingredients: TRL345 – Anti-Human Cytomegalovirus (HCMV) IgG1 κ Human Monoclonal Antibody	
Study Number: TRL345-102	Study Phase: Phase 1

Primary Objective:
 
Assess the safety and tolerability of TRL345 when administered intravenously (IV) as a single dose in healthy adult volunteers 
Secondary Objectives:
 
Characterize the pharmacokinetics (PK) of a single IV infusion of TRL345 overall and by DGAssess the immunogenicity of TRL345 as measured by anti-drug antibodies (ADAs) 
Exploratory Objectives:
 
Explore the pharmacodynamics (PD) of TRL345 in an ex vivo study using serum samples to explore the capacity of various concentrations of TRL345 to neutralize HCMV in human serumExplore if there are any differences in adverse events, clinical labs, or PK across dose groups to explore if there are any signs of off-target binding of TRL345	

Study Design

This is a Phase 1, first-in-human, double-blind, single ascending dose study to assess the safety, PK, PD, and preliminary activity of TRL345. Healthy subjects aged 18-65, inclusive, will be screened.

Subjects who meet all inclusion and no exclusion criteria, will be enrolled into the study, assigned to a dose group (DG), and randomized to receive TRL345 or placebo. Each DG will include 8 subjects; 6 will receive TRL345 and 2 will receive placebo. An established ELISA assay available in commercial laboratories to detect IgG antibodies against CMV will be used to determine serostatus of subjects prior to randomization. Dosing of the first two subjects (one randomized to TRL345 and one randomized to placebo) in each DG will be done on the same day. Dosing of the other subjects will occur at least 72 hours after the first two subjects have been dosed and following review of the blinded safety data from the first two subjects in the DG by the PI and Sponsor. After all subjects within a DG have completed Day 15, a Safety Monitoring Committee (SMC) will review all available safety data through Day 15 prior to making a recommendation regarding escalation to the next higher DG.

Subjects will be admitted to a Phase 1 research unit prior to the IV administration of a single dose of IP. In order to maintain the blind, subjects will be dosed as follows: DG1 will receive 1 mg/kg of TRL345 or 0.1mL/kg of placebo and DG2 will receive 10 mg/kg of TRL345 or 1mL/kg of placebo. All subjects (randomized to either TRL345 or placebo) will receive IP infused over 60 minutes.

Subjects will be closely monitored for AEs and SAEs, including infusion reactions (IRs), from the onset of the infusion through discharge from the Phase 1 research unit. Subjects will be assessed for safety and tolerability, including AEs and SAEs, at each follow-up visit after discharge through Day 76. A physical exam, vital signs, and routine clinical lab tests (chemistry and hematology) will be done on Days 1, 2, 3, 8, 15, 29, and 43. An ECG will be done on Days 1 and 8.

Serum for PK will be collected on Days 1 (0, 1, 2, 4, 6, 12 hours after start of infusion), 2 (24 hours after start of infusion) and 3 (48 hours after start of infusion), and on Days 8, 15, 29, 43 and 76. Additionally, serum samples will be taken on Days 1, 8, 29, 43 and 76 for measurement of anti-TRL345 antibody levels. Samples taken on Days 1, 43, and 76 will be analyzed using an electrochemiluminescence assay. Samples collected on Days 8 and 29 will be held for exploratory analysis, if warranted, based on Day 43 and Day 76 ADA analysis results. The proportion of subjects with detectable anti-TRL345 antibody responses prior to dosing and IP-emergent anti-TRL345 antibodies will be reported.

Additional serum samples will be collected on Days 1 (pre-infusion and 1 hour after start of infusion), 15, 29, 43, and 76 for *ex vivo* PD assessments, which will be conducted at [name] lab as defined in a separate protocol, whereby the dosed participants of the study will remain anonymous.

Additional serum samples will also be obtained on Days 1 (pre-infusion), 3, 8, 15, 29, and 43 for possible additional exploratory analyses that may be necessary to further explore any unexpected safety or tolerability observations.

Number of Subjects Planned: 16; 8 subjects will be randomized 6:2 (TRL345:placebo) to a DG (1 and 10 mg/kg doses)

Diagnosis and Main Eligibility Criteria:

Inclusion Criteria

1. Healthy male and non-pregnant, non-breast-feeding female subjects at between 18 and 65 years of age, inclusive, and representative of the general population
2. Willing and able to provide written informed consent.
3. Availability for the entire duration of the study, and willingness to adhere to protocol requirements
4. In good health, as determined by lack of clinically significant abnormalities in health assessments performed at the Screening Visit, as judged by the Principal Investigator (PI) or as delegated by the PI to a physician or nurse practitioner as sub-investigator.
5. Men and women of childbearing potential (WOCBP) must be willing to practice a highly effective method of contraception that may include, but is not limited to, abstinence, sex only with persons of the same sex, monogamous relationship with vasectomized partner, vasectomy, hysterectomy, bilateral tubal ligation, licensed hormonal methods, or intrauterine device (IUD) for 28 days before Screening and through Day 76. Men must also refrain from donating sperm from Day 1 through Day 76.

Exclusion Criteria

1. Inability to tolerate blood draws or has poor venous access
2. Body mass index (BMI) <18.5 or ≥ 35 kg/m²
3. Clinically significant vital sign abnormalities (systolic blood pressure lower than 90 or over 160 mmHg; diastolic blood pressure lower than 50 or over 100 mmHg; or, heart rate less than 45 or over 100 bpm) at the Screening Visit
4. ECG with clinically significant findings, including:
 - a. Conduction disturbance (complete left or complete right bundle branch block or nonspecific intraventricular conduction disturbance with QRS ≥ 120 msec, PR interval ≥ 220 msec, any second- or third-degree atrioventricular block, or prolongation of the QT interval corrected according to Fridericia's correction [>450 msec male and >460 msec female])
 - b. Significant repolarization (ST-segment or T-wave) abnormality; or
 - c. Significant atrial or ventricular arrhythmia; or
 - d. Frequent atrial or ventricular ectopy (e.g., frequent premature atrial contractions, 2 premature ventricular contractions in a row); or
 - e. ST-elevation consistent with ischemia or evidence of past or evolving myocardial infarction.

5. Presence of any gastrointestinal pathology (e.g., chronic diarrhea, inflammatory bowel diseases), unresolved gastrointestinal symptoms (e.g., diarrhea, vomiting), or progressive liver or kidney disease
6. Diagnosis of diabetes mellitus
7. History of acute or chronic pancreatitis or upper right quadrant postprandial discomfort or pain within the last 2 years
8. Clinically relevant medical conditions that, in the opinion of the PI, may interfere with the evaluation of the trial drug, e.g., progressive cardiovascular disease
9. Concurrent acute or chronic infections (e.g., viral infections, except chronic recurrent herpes simplex infections)
10. Significant abnormal safety labs, defined as:
 - Greater than 30% outside of the normal range for any of the following: hemoglobin, white blood cell (WBC) count, platelet count, neutrophil count and blood urea nitrogen
 - Aspartate aminotransferase (AST), alanine aminotransferase (ALT), alkaline phosphatase (ALP), direct bilirubin or indirect bilirubin $>2 \times$ the upper limit of normal
 - Activated partial thromboplastin time (aPTT) prolongation $>1.5 \times$ ULN
 - Hemoglobin A1C (HbA1C) $>5.6\%$
 - Fasting glucose level of ≥ 100 mg/dl (5.6 mmol/L)
 - Renal function based on the, i.e., estimated creatinine clearance < 70 mL/min (Cockcroft-Gault formula using ideal body weight)
 - Hemoglobin ≤ 128 g/L (males) and ≤ 115 g/L (females), and hematocrit $\leq 37\%$ (males) and $\leq 32.0\%$ for females
11. Positive test results for HIV, Hepatitis B (HBsAg), or Hepatitis C (HCV) at the Screening Visit
12. History of significant drug abuse within one year prior to the Screening Visit and/or ongoing
13. History of significant alcohol abuse within one year prior to the Screening Visit defined as more than fourteen units of alcohol per week [one “unit” is equal to approximately $\frac{1}{2}$ pint [200 mL] of beer, 1 small glass [100 mL] of wine, or 1 measure [25 mL] of spirits)
14. Positive test for drugs of abuse, ETOH and nicotine (cotinine) at the Screening Visit
15. Positive serum beta-human chorionic gonadotropin test for pregnancy, pregnant, or nursing women
16. Unwilling to refrain from donating blood or plasma during the study.
17. Use of any new prescription medication or over-the-counter (OTC) product (including natural food supplements, vitamins, herbs) within 14 days prior to dosing

18. Receipt of any vaccine or booster within 14 days prior to Day 1 or planned vaccination or booster within 4 weeks after IP administration
19. Any planned medical intervention or personal event that might interfere with the ability to comply with the study requirements
20. Is current study site staff paid entirely or partially by the contract for this trial, or staff who are supervised by the PI or sub-PI
21. Receipt of an investigational product, or participation in another trial involving a marketed or investigational drug within 30 days of Day 1, or 5 half-lives of the investigational drug, whichever is longer
22. Any other comorbidity or condition that, in the opinion of the Investigator would make the subject unsuitable for the study or unable to comply with the study requirements

Duration of Treatment: 1 dose. The total duration of the study is 76 days (approximately 11 weeks).

Test Product; Dose; and Mode of Administration: TRL345 administered by IV infusion.

- Dose level 1: 1 mg/kg
- Dose level 2: 10 mg/kg

Reference Therapy; Dose; and Mode of Administration: Normal saline, administered by IV infusion. To protect the blind, DG1 will receive 0.1 mL/kg and DG2 will receive 1 mL/kg.

Safety Monitoring:

Safety Monitoring Committee

A Safety Monitoring Committee (SMC) will review safety, dose escalation, and overall timelines. The SMC will review SAEs ([Section 7.2.2](#)) and \geq Grade 3 AEs that are “Likely” ([Section 7.2.3](#)) to be related to TRL345. Any infusion-related adverse event will be reported to the SMC within 24 hours. All data will be reviewed in an unblinded fashion upon completion of each DG.

Dose Escalation

The SMC will review all available safety data after the last subject in a DG has completed Day 15. They will evaluate the AEs, vital signs, and available laboratory results in the context of the established Study Pausing Rules (see below).

If Study Pausing Criteria are not met, the SMC will make one of the following recommendations:

- Escalate to the next higher dose as planned
- Expand the DG to obtain additional safety information based on possible trends in laboratory assessments or Grade 1 (Mild) adverse events

Study Pausing Rules

Should any one of the following criteria occur, the Sponsor will stop study recruitment and will not administer IP to any subject until the SMC has reviewed all available study data:

- First occurrence of an AE with severity Grade 3 (Severe) or Grade 4 (Potentially Life Threatening) considered to be at least likely related to TRL345
- 2 or more subjects with an AE of severity Grade 2 (Moderate) in the same body class considered to be at least likely related to TRL345 (among total number of subjects dosed)
- Any other toxicity which in the opinion of the SMC precludes further dosing.

Following review of safety data, the SMC will make a recommendation to continue the study as planned, to modify, or to terminate the study.

Criteria for Evaluation:

Safety:

- Incidence and severity of AEs (includes vital signs, ECGs, laboratory evaluations, and physical examination findings)
- Incidence of SAEs

PK: Serum concentrations of TRL345 will be determined by ELISA

Immunogenicity: Incidence of baseline and IP-emergent ADA (i.e., anti-TRL345 antibodies) in serum will determined by electrochemiluminescence assay

PD: Serum samples will be taken to explore the capacity of various concentrations of TRL345 to neutralize CMV in *ex vivo* assessments

Statistical Methods

Sample Size: No formal sample size calculations were performed. The numbers of subjects per DG are typical for Phase 1 studies in healthy adult volunteers.

Analyses:

Safety: Frequencies and percentages of subjects with AEs and SAEs will be summarized by dose group. Vital signs, ECGs, laboratory evaluations, and physical examination findings will be summarized with descriptive statistics by dose group. Additional serum samples will be taken and stored for possible exploratory analyses that may be necessary to further explore any unexpected safety or tolerability observations.

PK: Individual subject TRL345 serum concentrations and derived PK parameters will be summarized using descriptive statistics.

Immunogenicity: Anti-TRL345 antibodies will be summarized with descriptive statistics by DG.

PD: Serum samples will be taken and evaluated for *ex vivo* PD assessments.

SCHEDULE OF EVENTS

Study Day	Screening	1	2	3	8	15	29	43	76
Study Week					1	2	4	6	11
Window (days)	-8 (+/-6)	-1	0	0	± 1	± 3	± 3	± 3	± 5
Visit Type	A	RU	RU	RU	A	A	A	A	A
Procedure									
Informed Consent	X								
Eligibility	X	X ¹							
Demographics	X								
Medical/Disease History	X								
Complete Physical Exam	X								
Targeted Physical Exam		X ¹	X	X	X	X	X	X	
Vital Signs ²	X	X ³	X	X	X	X	X	X	
Weight	X	X ¹						X	
Height	X								
12-Lead ECG in triplicate ⁴	X	X			X				
Laboratory Tests									
Serum Chemistry ⁵	X	X ¹	X	X	X	X	X	X	
Hematology	X	X ¹	X	X	X	X	X	X	
Amylase, lipase, creatine kinase ⁶		X ¹		X	X	X			
Fasting glucose	X	X ¹		X	X	X	X	X	
HbA1C	X								
Fasting blood insulin level		X ¹		X	X	X	X	X	
Additional serum sample for possible exploratory analyses ⁷		X ¹		X	X	X	X	X	
NT-proBNP, IL-1 α		X ¹		X		X	X	X	
CMV Serology ⁸	X								
Serum Pregnancy Test (WOCBP)	X							X	
HIV, Hepatitis B, C Serology	X								
Urine Drug Test	X								
Randomization		X ¹							
Dosing of IP (TRL345 or placebo)		X							
PK sampling – serum ⁹		X	X	X	X	X	X	X	X
PD sampling – serum ¹⁰		X				X	X	X	X
ADA sampling – serum ¹¹		X ¹			X		X	X	X
Adverse Events		X	X	X	X	X	X	X	X
Concomitant Medications		X ¹	X	X	X	X	X	X	X
Overall Status								X	X

Visit Type: A = ambulant, RU = Research Unit, NA = phone call

- To be performed prior to the administration of IP.
- Vital signs include temperature, blood pressure, and heart rate. Vital signs should be obtained after subject is resting for 5 minutes. The window for all vital signs is ± 10 minutes.
- On Day 1, vital signs will be obtained within 60 minutes prior to dosing, at 15, 30, and 60 minutes (end of the infusion), and 1 hour and 4 hours after the end of the infusion.

4. Subjects may not use tobacco or nicotine within 4 hours prior to the ECG. ECG on Day 1 will be performed within 4 hours after completion of the infusion.
5. Serum chemistry at Days 1, 15, and 29 is to include hsCRP and LDH.
6. Subjects must refrain from strenuous exercise within 5 days prior to assessment of creatine kinase
7. An additional 5 mL serum sample will be collected immediately prior to the IP infusion on Day 1 and on Days 3, 8, 15, 29, and 43 and stored for possible exploratory analyses.
8. An established ELISA assay available in commercial laboratories to detect IgG antibodies against CMV will be used to determine serostatus of subjects.
9. Samples for PK will be collected immediately prior to the IP infusion on Day 1 and end of the infusion (60 minutes) \pm 15 minutes, and hours 2 \pm 15 minutes, 4 \pm 15 minutes, 6 \pm 15 minutes, 12 \pm 1 hour, 24 (Day 2) \pm 1 hour, and 48 (Day 3) \pm 1 hour after start of infusion and then on Days 8, 15, 29, 43, and 76.
10. Samples for PD will be collected immediately prior to the IP infusion on Day 1 and end of the infusion (60 minutes) \pm 15 minutes and on Days 15, 29, 43, and 76 for *ex vivo* PD assessments.
11. Samples for ADA will be collected immediately prior to the IP infusion on Day 1 and on Days 8, 29, 43, and 76. ADA samples collected on Days 8 and 29 will be held for exploratory analysis, if warranted.

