2.2 Endpoints

2.2.1 *Safety Endpoints*

- Incidence and severity of abnormal physical exam findings, serum chemistries and hematology, vital signs (temperature, blood pressure, heart rate), adverse events, and incidence of serious adverse events

2.2.2 *Pharmacokinetics*

- C_{max} , C_{min} , CL, Vss, and T1/2 overall and by DG will be determined by ELISA

2.2.3 *Immunogenicity*

- Incidence of baseline and IP-emergent ADA (i.e., anti-TRL345 antibodies) in serum will be determined by ELISA

2.2.4 *Pharmacodynamics*

- The proportion of samples with TRL345 concentrations within prespecified ranges that are associated with neutralization of HCMV in human serum

2.2.5 *Exploration of Possible Off-Target Binding*

- Gastrointestinal and CNS adverse events will be compared across DGs for any qualitative or quantitative differences in such events. LDH, hsCRP, IL-1alpha, estimated AUC, and estimated T1/2 will also be compared across DGs.

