3 STUDY DESIGN

3.1 Overall Study Design

This is a Phase 1, first-in-human, double-blind, single ascending dose study to assess the safety, PK, and PD of TRL345 in approximately 16 healthy male and female volunteers. Subjects aged 18-65, inclusive, will be screened.

Subjects will be assigned to a DG and randomized to receive TRL345 or placebo. There will be two dose groups. Each DG will be composed of 8 healthy volunteers; of these 6 will be randomized to receive TRL345 and 2 will be randomized to placebo. Any subject who withdraws before completing the study but after receiving IP may be replaced at the discretion of the Sponsor and in consultation with the Investigator. Any replacement subject will be assigned to receive the same treatment as the subject he or she is replacing.

An established ELISA assay available in commercial laboratories to detect IgG antibodies against CMV will be used to determine serostatus of subjects.

Dosing of the first two subjects (one randomized to TRL345 and one randomized to placebo) in each DG will be done on the same day. Dosing of the other subjects will occur at least 72 hours after the first two subjects have been dosed and following review of the blinded safety data from the first two subjects in the DG by the PI and Sponsor. After all subjects within a DG have completed Day 15, a Safety Monitoring Committee (SMC) will review all available safety data through Day 15 prior to making a recommendation regarding escalation to the next higher DG.

Subjects will be admitted to a Phase 1 research unit prior to the IV administration of a single dose of IP. In order to maintain the blind, subjects will be dosed as follows: DG1 will receive 1 mg/kg of TRL345 or 0.1mL/kg of placebo and DG2 will receive 10 mg/kg of TRL345 or 1mL/kg of placebo. All subjects (randomized to either TRL345 or placebo) will receive IP infused over 60 minutes.

Subjects will be closely monitored for AEs and SAEs, including infusion reactions (IRs), from onset of the infusion through discharge from the Phase 1 research unit. Subjects will be assessed for safety and tolerability, including AEs and SAEs at each follow-up visit after discharge through Day 76. A physical exam, vital signs, and routine clinical lab tests (chemistry and hematology) will be done on Days 1, 2, 3, 8, 15, 29, and 43. An ECG will be done on Days 1 and 8.

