3.5 Dose Escalation Criteria

The SMC will review all available safety data after the last subject in a DG has completed Day 15. They will evaluate the AEs, vital signs, and available laboratory results in the context of the established Study Pausing Rules (see below).

If Study Pausing Criteria are not met, they will make one of the following recommendations:

- Escalate to the next higher dose as planned
- Expand the DG to obtain additional safety information based on possible trends in laboratory assessments or Grade 1 (Mild) adverse events

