6.1 Definitions and Descriptions of Assessments and Procedures

Medical history – medical history will be obtained by way of subject interview and medical records. All clinically significant past and current medical history will be obtained. Clinically significant history includes those illnesses/diagnoses that are/were treated with medication for more than 14 days or other medical intervention (e.g., hospitalization, surgery, physical therapy, etc.).

Complete physical exam – examination of the following systems: ear, nose, and throat; cardiovascular; respiratory; gastrointestinal; musculoskeletal; dermatological; neurological; and confirmation of venous access.

Targeted physical exam – brief, focused examination of the subject following medical history, including assessment for AEs.

12-lead ECG – after a subject has been supine for 5 minutes, triplicate ECGs will be obtained over 5 minutes. The investigator will interpret the ECG using 1 of the following categories: normal, abnormal but not clinically significant (NCS), or abnormal and clinically significant (CS). QTcF will also be determined. Subjects may not use tobacco or nicotine within 4 hours prior to the ECG.

Vital Signs – temperature, heart rate, blood pressure. Heart rate and blood pressure should be obtained after subject is resting for 5 minutes. Height will be obtained at Screening only. Weight will be obtained at Screening, on Day 1, and at Day 43.

Serum chemistry – sodium, potassium, chloride, carbon dioxide (CO₂), urea nitrogen (BUN), creatinine (CREA), calcium, glucose, total protein, albumin, total bilirubin, alkaline phosphatase, aspartate aminotransferase (AST), alanine aminotransferase (ALT). HsCRP and LDH will be assessed at Days 1, 15, and 29 only.

Hematology – hemoglobin, red blood cell count, white blood cell count with differential, platelet count.

Hemoglobin A1c – whole blood sample at Screening

Additional safety assessments – amylase, lipase, creatine kinase, NT-proBNP, IL-1 α , fasting glucose, fasting blood insulin. Subjects must refrain from strenuous exercise within 5 days prior to assessment of creatine kinase.

CMV serology – an established ELISA assay available in commercial laboratories to detect IgG antibodies against CMV will be used to determine serostatus of subjects.

Urine drug test – amphetamines (includes methamphetamines and ecstasy/methylenedioxymethamphetamine), barbiturates, benzodiazepines, cannabinoids, cocaine

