6.4 On-Study Procedures

6.4.1 Study Day 1

The following procedures will be performed prior to administration of IP:

Reconfirm eligibility

Targeted physical exam

Concomitant medication assessment

Laboratory Evaluations, including:

- Serum chemistry (including hsCRP and LDH)
- Hematology
- Amylase, lipase, and creatine kinase (subjects must refrain from strenuous exercise within 5 days prior to assessment of creatine kinase)
- Fasting glucose
- Fasting blood insulin level
- NT-proBNP and IL-1 α
- Serum for PK, PD, ADA, and possible exploratory analyses (see additional times below for PK and PD)

The following procedures will be performed at the times specified below:

Vital signs within 60 minutes prior to dosing and then at 15, 30, and 60 minutes (end of the infusion), and 1 and 4 hours after the end of the infusion

Serum for PK will be obtained at prior to the start of infusion and then at end of infusion (60 minutes), and 2, 4, 6, 12, 24 (Day 2), and 48 hours (Day 3) after the start of the infusion

Serum for PD will be obtained at prior to start of infusion and then at end of infusion (60 minutes)

12-lead ECGs in triplicate within 4 hours post-completion of infusion (subjects may not use tobacco or nicotine within 4 hours prior to the ECG)

Additionally, the following will be performed:

Randomization of the subject to study/DG

Intravenous dosing of study IP per randomization assignment. A calibrated IV infusion pump will be set to deliver the total volume of IP over a 60-minute period.

Adverse events will be assessed during and after the infusion.

6.4.2 Study Days 2 and 3

The following procedures will be performed:

Targeted physical exam

Vital signs

Laboratory Evaluations, including:

- Serum chemistry
- Hematology
- Amylase, lipase, and creatine kinase (subjects must refrain from strenuous exercise within 5 days prior to assessment of creatine kinase) (Day 3 only)

- Fasting glucose (Day 3 only)
- Fasting blood insulin level (Day 3 only)
- Additional serum sample for possible exploratory analyses (Day 3 only)
- NT-proBNP and IL-1 α (Day 3 only)
- Serum for PK

AE assessment

Concomitant medication assessment

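### hsCRP and LDH, two of the three laboratory analytes named for off-target binding, have no post-dose value until Day 15, so a transient early change in them would be missed

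*Protocol*

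**What the plan says.** The exploratory off-target endpoint in Protocol Section 2.2.5 has two parts. The first is clinical: "Gastrointestinal and CNS adverse events will be compared across DGs for any qualitative or quantitative differences in such events". The second covers laboratory and PK measures: "LDH, hsCRP, IL-1alpha, estimated AUC, and estimated T1/2 will also be compared across DGs". SAP Section 2 repeats both.

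The sampling days for hsCRP and LDH are stated consistently. Schedule of Events, footnote 5: "Serum chemistry at Days 1, 15, and 29 is to include hsCRP and LDH". Section 6.1 is firmer: "HsCRP and LDH will be assessed at Days 1, 15, and 29 only". In Section 6.4.1 the Day 1 chemistry, with both markers, falls under the heading "The following procedures will be performed prior to administration of IP", so it is a baseline value. SAP Section 8.5 marks the two analytes at baseline, Day 15 and Day 29 only.

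Chemistry itself is drawn more often. Section 3.1 says that "routine clinical lab tests (chemistry and hematology) will be done on Days 1, 2, 3, 8, 15, 29, and 43". IL-1alpha, the third named laboratory analyte, has a Day 3 sample (Schedule of Events; Section 6.4.2).

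Two dosing decisions depend on early safety data. Under Section 3.1 the remaining subjects in a dose group may be dosed from 72 hours after the first two, following blinded safety review. Under Section 3.5, "The SMC will review all available safety data after the last subject in a DG has completed Day 15".

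**The concern.** Section 1.3.1 concedes that adverse off-target binding cannot be excluded, and Section 2.2.5 selects the laboratory analytes with which to look for it. Two of the three are then not measured for the first two weeks after a first-in-human infusion, although the chemistry sample that could carry them is taken three times in that period. The protocol gives no reason for starting them at Day 15.

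Two things are at stake. The exploratory comparison of hsCRP and LDH across dose groups would rest on Days 15 and 29 alone and would say nothing about a short-lived early change. The sentinel and escalation reviews would also be made with none or little of the information that the protocol itself calls relevant. Section 3.5 allows the committee to recommend expanding a dose group on possible laboratory trends, and a single post-dose value gives little basis for judging one.

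**Working it through.** The plan has no calculated figure to reproduce here: Section 8.1 says no formal sample size calculation was made, and the point concerns a visit schedule. The check sets the schedules side by side and counts.

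**1. Post-dose sampling days** (Schedule of Events; Sections 6.4.2 to 6.4.5; SAP 8.5)

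| Measure | Post-dose days | Before Day 15 |
|---|---|---|
| Routine chemistry (includes AST, ALT, alkaline phosphatase, bilirubin) | 2, 3, 8, 15, 29, 43 | 3 draws |
| IL-1alpha, NT-proBNP | 3, 15, 29, 43 | 1 |
| Amylase, lipase, creatine kinase | 3, 8, 15 | 2 |
| hsCRP, LDH | 15, 29 | 0 |

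The two markers are on 2 of 6 post-dose chemistry draws and on 0 of the 3 before Day 15.

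**2. Time to the first post-dose value.** (15 − 1) × 24 = 336 h nominal. The Schedule of Events gives Day 15 a window of ±3 days, so 264 to 408 h. Section 6.4.4 gives ±2 days, so 288 to 384 h. These two windows disagree and need reconciling, but under either the earliest value is 11 days or more after dosing (264 / 24 = 11).

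**3. What the two reviews would hold.**

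- Sentinel review: at the 72-hour minimum, neither marker has a post-dose value. The Day 3 chemistry is drawn at a nominal 48 h, which is 72 − 48 = 24 h earlier. A value from that draw could inform the review if the laboratory reports in time; turnaround is not stated.
- Escalation review: the last subject dosed has one post-dose value, from the gating visit itself. Another subject has a Day 29 value by then only if dosed, on nominal timing, at least 29 − 15 = 14 days before the last one. The required stagger is only 72 h (3 days). Even then, Section 3.1 describes a review of data through Day 15, which may exclude Day 29 values.

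**4. How much of a transient rise would remain at Day 15.** The documents give no marker kinetics, so this is an illustration with an assumed return half-time h. Share remaining at 336 h = 2^(−(336 − peak time)/h).

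| Assumed h | Peak at 48 h (Day 3) | Peak at 168 h (Day 8) |
|---|---|---|
| 24 h | 0.02% | 0.8% |
| 48 h | 1.6% | 8.8% |
| 96 h | 12.5% | 30% |
| 168 h | 30% | 50% |

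Example: peak at 48 h and h = 96 h gives 2^(−288/96) = 2^(−3) = 12.5%. A fast-resolving rise is essentially gone by Day 15; a slow one may still show.

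**5. After the change.** With Days 3 and 8 added, post-dose time points go from 2 to 4 and the first value moves from 336 h to 48 h.

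**The case against.** The strongest reply is that the schedule is deliberate and consistent, serves an exploratory objective, and leaves off-target effects well covered early on. Much of this stands:

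- Before Day 15 the trial collects adverse events at every visit, IL-1alpha and NT-proBNP on Day 3, amylase, lipase and creatine kinase on Days 3 and 8, and liver tests and blood counts on Days 2, 3 and 8. Section 1.3.1 places the main risk in gastrointestinal tissue and pancreas, which adverse events and pancreatic enzymes address directly. A reader might infer that no early off-target signal could be seen at all; the documents do not support that.
- Different markers have different days throughout the schedule, so a Day 3 sample for one does not prove that Day 3 is needed for another. Whether a rise would vanish by Day 15 depends on kinetics that the documents do not give.
- No pausing criterion in Section 3.6 is tied to hsCRP or LDH.
- With 6, 6 and 4 subjects (two active groups and pooled placebo), a null descriptive comparison would remain weak evidence even with more time points.
- Extra serum is stored on Days 3 and 8 (footnote 7), and Section 6.5 permits laboratory testing of stored samples for safety.

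The last point does not close the gap. The stored serum is for possible follow-up of unexpected safety or tolerability observations. A silent laboratory change would not prompt such testing, and nothing times it to either dosing decision.

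A reader might also apply the 46-hour rat half-life in Section 1.3.2 and conclude that the drug has gone by Day 15. That does not follow. The figure is for rats, the text gives no human half-life, and PK sampling runs to Day 76. The point does not need it.

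**Conclusion.** The point holds as a gap in two named markers. hsCRP and LDH have no post-dose value for a nominal 336 hours, on 0 of 3 available chemistry draws, while their companion IL-1alpha is sampled on Day 3. A transient early change in either would be missed; a sustained or slowly resolving one could still appear at Day 15. How much would be lost depends on assumed return half-times: from nearly all of a rise to about half of it over the range shown.

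The 72-hour sentinel review has neither marker. The escalation review may have only one post-dose value for later-dosed subjects. One might read this as at most one value for everyone, but that is certain only for late-dosed subjects, or if the review is cut at Day 15, since Section 3.5 sets no such cut-off.

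This is not an internal contradiction or an error in the analysis. It is an inexpensive improvement to an exploratory objective, and it could also help two dosing decisions.

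**What to change.** Add hsCRP and LDH to the chemistry already drawn on Days 3 and 8. Day 3 matches IL-1alpha and precedes the 72-hour point. Align footnote 5 of the Schedule of Events, the sentence in Section 6.1 that limits the two tests to three days, Sections 6.4.2 and 6.4.3, and the asterisked time points in SAP Section 8.5. If the sponsor prefers the present schedule, the protocol should say why Day 15 is the first informative time.

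Cost: 2 analytes × 2 visits × 16 subjects = 64 assays, with no new visit or procedure. Including Day 2 as well would make 2 × 3 × 16 = 96. Replacement subjects or an expanded dose group would add in proportion. The other downside is a few more incidental out-of-range values to review.

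In the same edit, reconcile the Day 15 visit window between the Schedule of Events and Section 6.4.4.
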